9.2 Leukapheresis

Leukapheresis for AGS-003 manufacturing will be performed at the American Red Cross according to the Argos Leukapheresis Manual and sent directly to Argos on the day of collection.

9.3 Nephrectomy

Fresh tissue will be obtained from the surgical specimen to evaluate the effect of AGS-003 treatment. Samples to be taken are primarily tumor tissue, but may also include normal kidney, adrenal gland, lymph nodes, and /or surrounding tissues as included in the resection. The minimum amount needed is 1g and optimum is 10 grams but additional amounts will be accepted if not required for other institutional research.

The fresh tissue will be sent to [name] laboratory for processing:

Buffalo Life Sciences Complex (BLSC)
Center for Genetics and Pharmacology (CGP)
Laboratory location: L5-141
Lab [contact]

Lab contacts:

[name] [name] PhD-Lab Manager
[name], Assistant Professor, office number: [contact]
[name] [contact]
[name] office number: [contact]
[name] [contact]

For historical comparison, the RCC TMA in existence will be used.

Note: All investigator or analyzing research laboratories housing research samples need to maintain current **Temperature Logs** and study-specific **Sample Tracking and Shipping Logs**. The Principal Investigator/Laboratory Manager **must** ensure that the stated lab(s) have a process in place to document the receipt/processing/storage/shipping of study-related samples/specimens. This is required for both observational and interventional clinical studies collecting clinical samples.

Nephrectomy tissue will also be sent to Argos. Kit for tissue will be provided for each patient by Argos. Sample will be sent to CRS Lab Path Team for processing and shipping. Please see Argos Tumor Worksheet

Tumor Specimen Collection Guidelines for Argos

1 The tumor specimen biopsied must represent viable, non-necrotic tissue that is at least 70% tumor

2 Prepare tumor specimen by completing four (4) biopsy passes for each vial of RNA preservative using 16 gauge or 18 gauge biopsy needles.

NOTE: DO NOT place the specimen in formalin or any other fixative.

NOTE: DO NOT use absorbent material while preparing the tumor specimen.

3 Place the tumor specimen into the RNA preservative vial(s), cap, and gently swirl to separate specimen pieces and adequately immerse specimen pieces in preservative.

NOTE: Only use RNA preservative vials provided with this kit.

4 The tumor specimen should be shipped at room temperature the same day as collection. If the shipment cannot go out the same day as collection, the sealed kit with the tumor specimen in it must be stored in a 2-8° C refrigerator until ready for shipment.

9.4 Pathology

9.4.1 Pre-Treatment Formalin-Fixed Paraffin Embedded (FPPE) Biopsy Samples

The following sections of tissue from the most recent (Screening) renal cell tissue biopsy (neoplastic) that exists in the Paraffin Archive in the Department of Pathology will be collected:

- Ten (10) unstained sections cut at 5 microns on plus glass slides.

The study coordinator or designee will be responsible for entering the order into the EMR using the standard format for all clinical trial pathology requirements.

9.4.2 Post-Treatment Resection Formalin-Fixed Paraffin Embedded (FPPE) Samples

The following sections of tissue from the end of treatment nephrectomy (primarily tumor tissue, but may also include normal kidney, adrenal gland, lymph nodes, and /or surrounding tissues) that exists in the Paraffin Archive in the Department of Pathology will be collected:

- Ten (10) unstained sections cut at 5 microns on plus glass slides.

The study coordinator or designee will be responsible for entering the order into the EMR using the standard format for all clinical trial pathology requirements.

Once the samples have been processed by the Pathology Department at RPCI, they will be sent to [name] laboratory:

Buffalo Life Science Complex (BLSC)
Center for Genetics and Pharmacology (CGP)
Laboratory location: L5-141
Lab [contact]

Lab Contacts:

[name]

[name], Assistant Professor, office number: [contact]

[name] [contact]

[name] office number: [contact]

[name] [contact]

Slides will be shipped by the investigator to Adaptive Biotechnologies, Seattle Washington, for analysis.

Note: All investigator or analyzing research laboratories housing research samples need to maintain current **Temperature Logs** and study-specific **Sample Tracking and Shipping Logs**. The Principal Investigator/Laboratory Manager **must** ensure that the stated lab(s) have a process in place to document the receipt/processing/storage/shipping of study-related samples/specimens. This is required for both observational and interventional clinical studies collecting clinical samples.

10 SAFETY EVALUATION

Safety will be assessed through physical examinations, medical history, clinical laboratory tests, vital sign assessments, and evaluation of adverse events (AEs). Assessments will include grading of the frequency and severity of AEs associated with the treatment, including but not limited to clinical laboratory values, autoimmunity evaluations, and evaluations of injection site reactions (ISRs).

10.1 Medical History

During study Pre-treatment, a complete medical history will be obtained that includes medical and oncologic history, demographics (date of birth, sex, race, ethnicity), history of other disease process (active or resolved), medication history, and concomitant illness. The medical history must be documented in the subject's chart.

10.2 Physical Examination

A physical exam that includes a complete review of major body systems and vital signs will be performed by the investigator or designee during Pre-treatment and at the End of Study/Follow-up visit. Vital sign measurements to be obtained include systolic and diastolic blood pressure, heart rate, weight, height (at Pre-treatment only), body temperature, and respiratory rate.

10.3 Autoimmunity Assessments

Autoimmune laboratory parameters (i.e. RF, TG, dsDNA antibody, ANA) will be followed for shifts from Screening assessment on Injection Week #1 (prior to dosing), Injection Week #3

(prior to dosing), Nephrectomy Visit (either at pre-operative visit or on day of nephrectomy prior to surgery), and at End of Study/ Follow-Up visit. Autoimmunity results from the laboratory will be assessed by the investigator for clinical significance. Abnormal laboratory parameters, even as assessed as clinically non-significant, will require closer examination for other indications of clinically manifested autoimmune disease. Abnormal laboratory parameters will be followed by clinical evaluations and repeated laboratory assessments as indicated by the investigator. Clinically confirmed occurrences of autoimmunity will be reported expeditiously to Argos Therapeutics. Any subject who develops autoimmune disease will be withdrawn from the study (refer to **Section 6.5**).

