6.1.2 Leukapheresis

The AGS-003 manufacturing process requires leukapheresis to collect autologous leukocytes. Study patients will be referred to the American Red Cross in Buffalo ([name]). Even though leukapheresis occurs prior to administration of investigational product, RPCI will report to the FDA severe (Grade 3, CTCAE) or life-threatening (Grade 4, CTCAE) events associated with the leukapheresis.

The leukapheresis should not be performed less than 48 hours after the tumor biopsy procedure (Section 6.1.1).

In most cases, only a single leukapheresis will be required to support product manufacture. However in some cases, cellular collection or manufacturing with the initial product is unsuccessful, and a second or third leukapheresis may be required. If additional leukapheresis (es) is required, standard treatment should still be initiated as clinically indicated.

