8.2 Screening

The following evaluations will be performed within 4 weeks prior to tumor biopsy:

- Medical history (including all prior anti-tumoral therapy related to RCC)

- Physical examination, including vital signs (i.e., temperature, heart rate, respiratory rate, blood pressure), body weight, and height
- Hematology:
 - (i.e., complete blood count (CBC) with automated differentials): WBC, RBC, HGB, HCT, platelet, MCV, MCH, MCHC, %neutrophils, absolute neutrophils, %monocytes, absolute monocytes, %eosinophils, absolute eosinophils, %basophils, absolute basophils, %lymphocyte total, absolute lymphocyte total, platelet confirmation (as clinically indicated), and differential confirmation (as clinically indicated).
- Chemistry:
 - Complete Metabolic Panel (i.e., CMP: chloride, CO₂, potassium, sodium, BUN, glucose, calcium, creatinine, total protein, albumin, bilirubin total, alkaline phosphatase, AST, ALT, osmol (calc), anion gap, B/C ratio, A/G ratio) along with gamma-glutamyl transferase (GGT), lactose dehydrogenase (LDH), phosphorus, magnesium, uric acid, thyroid stimulating hormone (TSH), c-reactive protein (CRP), and corrected calcium.
- Autoimmunity Assessment:
 - Rheumatoid factor (RF)
 - Anti-thyroglobulin antibody (TG)
 - Anti-double stranded DNA antibody (dsDNA antibody)
 - Anti-nuclear antibody (ANA)
- ECOG Performance Status (see **Appendix A**)
- Tumor assessment, including CT scan of the chest, abdomen, and pelvis
- Concomitant Medications List any ongoing medications with an onset within 1 week of tumor biopsy
- Pregnancy test (urine) in females of childbearing potential

Tumor biopsy for AGS-003 in accordance with Argos requirements will also be performed at Screening.

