8.3 Leukapheresis Visit (must occur within 3 weeks after biopsy)

Leukapheresis: Leukapheresis for AGS-003 manufacturing should be performed 3 weeks after tumor biopsy. Scheduling of leukapheresis will be determined by American Red Cross availability. Patient may need second leukapheresis based on success of first one. All efforts will be made to ensure that second leukapheresis will be within the 3 week timeframe but will not be considered a protocol deviation if it falls out of this window.

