8.4 AGS-003 Treatment Phase

The manufacturing of the vaccine can take 6-12 weeks. Due to the unexpected nature of the timeline of manufacturing, once the vaccine has been successfully created and ready to be shipped to RPCI, the study coordinator will work with Argos and all site staff to ensure that scheduling for proper administration and safety testing is performed. Injections should be given 7 days apart. Shipments are sent from Argos one dose at a time. Shipment delays and other unexpected events do occur therefore a dosing window of +/- 2 days will be allowed for each dose.

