8.4.1 Injection Week #1

- Vital Signs, weight
- ECOG Performance Status
- Concomitant medications
- Adverse events
- Hematology, Chemistry, Autoimmune and Immunologic assessment prior to dosing
- Administer AGS-003, 1st dose

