8.6 Schedule of Procedures and Observations

The schedule of procedures and observations for this study is summarized in **Table 1**.

Table 1. Schedule of Procedures and Observations

	Screening ¹	Leukapheresis Visit	Injection Week #1	Injection Week #2	Injection Week #3	Nephrectomy Visit	End of Study/ Follow -Up ³
Medical History	X						
Physical Examination	X						X
Vital Signs & ECOG ¹³	X		X	X	X		X
Prior/Concomitant Medications	X ⁴		X	X	X	X	X
Adverse Events			X	X	X	X	X
Chemistry ⁵	X		X		X	X	X
Hematology ⁶	X		X		X	X	X
Autoimmunity Assessment ⁷	X		X		X	X	X
Pregnancy Test (urine) ⁸	X						X
Tumor Assessment ⁹	X						
Tumor Biopsy for AGS-003	X						
Leukapheresis for AGS-003 ¹⁰		X					
AGS-003 Dose ¹¹			1 st	2 nd	3 rd		
Blood Sampling for Immunologic Assessment ¹²			X			X	X
Nephrectomy						X	
Tissue from Nephrectomy						X	

Notes for Table 1

1. Performed within 4 weeks prior to Leukapheresis Visit.
2. If there is a pre-operative visit, Nephrectomy Visit assessments may be performed as part of that visit instead. Otherwise, assessments, including immunologic, are to be performed on day of nephrectomy prior to surgery.
3. Performed at post op visit following nephrectomy, or if subject discontinues or is withdrawn from the study.
4. Medications ongoing within 1 week prior to tumor biopsy.
5. **Chemistry:** Complete Metabolic Panel (i.e., CMP: chloride, CO₂, potassium, sodium, BUN, glucose, calcium, creatinine, total protein, albumin, bilirubin total, alkaline phosphatase, AST, ALT, osmol (calc), anion gap, B/C ratio, A/G ratio) along with gamma-glutamyl transferase (GGT), lactose dehydrogenase (LDH), phosphorus, magnesium, uric acid, thyroid stimulating hormone (TSH), c-reactive protein (CRP), and corrected calcium. NOTE: On Injection Weeks #1 and #3 assessments should be taken prior to dosing. At Nephrectomy Visit the assessments can be taken either at a pre-operative visit or on the day of nephrectomy prior to surgery.

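### Autoimmunity shifts are referenced to Screening, at least about 6 weeks before the first dose, although the same markers are drawn just before that dose

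*Combined protocol and SAP*

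**What the plan says.** Section 10.3 names four laboratory markers (RF, TG, dsDNA antibody and ANA) that "will be followed for shifts from Screening assessment on Injection Week #1 (prior to dosing), Injection Week #3", followed by the Nephrectomy Visit and End of Study. Screening is the only reference point it gives. It does not define a shift or say how shifts are to be summarised, and Section 12 does not mention them.

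A sample just before treatment already exists. Section 8.4.1 lists "Hematology, Chemistry, Autoimmune and Immunologic assessment prior to dosing", and Table 1 with its note 7 schedules the same four markers at that visit.

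The timing of Screening is given in two ways. Section 8.2 says "The following evaluations will be performed within 4 weeks prior to tumor biopsy", whereas note 1 of Table 1 says "Performed within 4 weeks prior to Leukapheresis Visit". Between Screening and the first dose come the biopsy, one or more leukaphereses, and manufacture: "The manufacturing of the vaccine can take 6-12 weeks".

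**The concern.** A shift is useful in a safety review when it helps to tell change after the drug from change before it. The first shift listed in Section 10.3, at Injection Week #1 before dosing, cannot be an effect of AGS-003. The later ones combine the untreated wait with the treated period.

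This can mislead in both directions. A marker that turns positive during the wait and stays positive appears as a shift at every later visit, with nothing having changed on treatment. A marker that is positive at Screening, negative before dose 1 and positive again afterwards shows no net shift from Screening after dosing. The second pattern can occur because the note to exclusion criterion 6 admits patients with abnormal autoimmunity markers and no other signs or symptoms of autoimmune disease.

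What is at stake is attribution. Section 7.2 lists a systemic autoimmune response among the theoretical risks, and these four markers are the panel designated to look for it.

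**Working it through.** The plan states no Screening-to-dose interval, so there is no figure to reproduce. It has to be built from the windows.

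**Inputs**
- Screening to biopsy: 0 to 4 weeks (Section 8.2).
- Screening to leukapheresis, alternative window: at most 4 weeks (Table 1, note 1).
- Biopsy to leukapheresis, minimum: "The leukapheresis should not be performed less than 48 hours after the tumor biopsy procedure" (Section 6.1.2). This is 2/7 = 0.3 week.
- Biopsy to leukapheresis, maximum: 3 weeks (heading of Section 8.3). The sentence beneath reads differently: "Leukapheresis for AGS-003 manufacturing should be performed 3 weeks after tumor biopsy".
- Manufacture: 6 to 12 weeks (Section 8.4). The start of this clock is not stated.
- Assumption: the first dose follows the end of manufacture at once.

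**Screening to dose 1, in weeks**

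| Reading | Shortest | Longest |
|---|---|---|
| Section 8.2 window, manufacture from leukapheresis | 0 + 0.3 + 6 = 6.3 | 4 + 3 + 12 = 19 |
| Table 1 note 1 window, manufacture from leukapheresis | 0.3 + 6 = 6.3 | 4 + 12 = 16 |
| Section 8.2 window, manufacture from biopsy | 0 + 6 = 6 | 4 + 12 = 16 |
| Section 8.2 window, leukapheresis exactly 3 weeks after biopsy | 0 + 3 + 6 = 9 | 4 + 3 + 12 = 19 |

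Section 6.5 removes a patient only when product is delayed by more than 2 weeks, so a tolerated delay could take the longest case to 19 + 2 = 21 weeks. A repeat leukapheresis outside the 3-week window could extend it further. On every reading the wait is at least about 6 weeks.

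**Share of elapsed time before dose 1.** With a wait of *s* weeks and a visit *v* weeks after dose 1, the share is s / (s + v).
- Injection Week #3 (v = 2, nominal): 6.3/8.3 = 76%; 16/18 = 89%; 19/21 = 90%.
- End of Study: the interval from dose 3 to nephrectomy is not stated. Assuming 1 week, and about 4.3 weeks from nephrectomy to End of Study (Section 8.5 says roughly one month), v = 2 + 1 + 4.3 = 7.3. The shares are 6.3/13.6 = 46%; 16/23.3 = 69%; 19/26.3 = 72%.

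These are shares of time, not of shifts. The documents give no rate at which these markers change without treatment.

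**What each reference shows at a visit after dosing**

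| Screening | Week #1 pre-dose | After dosing | From Screening | From Week #1 |
|---|---|---|---|---|
| negative | positive | positive | shift | no shift |
| positive | negative | positive | no shift | shift |
| negative | negative | positive | shift | shift |

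The two references disagree exactly where the marker changed during the wait. With the Week #1 value as reference, the gap between baseline and first dose becomes zero, and the Week #3 comparison covers about 2 weeks, all after dose 1.

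**The case against.** The strongest reply is that nothing in the plan depends on the choice, and much of this stands.

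- **No shift is counted.** A reader might infer that pre-treatment changes will be tallied as on-study or drug-related shifts. The documents do not say so. Section 12.3 plans adverse event proportions only, and under Section 10.5.4 a laboratory abnormality becomes an adverse event only if it is clinically significant and needs active management.
- **The pre-dose change can be seen.** Injection Week #1 is its own time point in Section 10.3. With at most 10 patients and five scheduled values per marker, a reader of the listings can see when a marker changed. To say that the rule conceals a signal would go too far.
- **Clinical action does not use the shift.** Closer examination is triggered by an abnormal value, even one judged not clinically significant. Withdrawal and expedited notice to the manufacturer depend on clinically confirmed autoimmunity. Neither depends on the baseline.
- **The panel is not the only relevant laboratory information.** TSH and CRP are in the chemistry panel. No Screening-referenced shift is specified for chemistry or hematology, so the point does not extend to them.
- **Screening is a defensible reference for general monitoring.** It precedes the biopsy and leukapheresis, and serious adverse events are reported from consent.

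The reply does not remove the narrower point. Section 10.3 states a reference, it is Screening for every later visit, and no passage designates the pre-dose value as the baseline for on-treatment change. Routine adverse event reporting starts with the intervention (Section 10.7), and immunologic sampling starts just before dose 1 (Section 9.1.1). The autoimmunity reference differs from both, and no reason is given.

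**Conclusion.** The point holds as a low-cost improvement to a descriptive safety read-out. Shifts from Screening at Injection Week #3, nephrectomy and End of Study do not separate change before treatment from change after it, and a better reference is already collected.

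The wait is derived, not stated: about 6 to 19 weeks from Sections 8.2 to 8.4, or at most 16 weeks under Table 1 note 1. Both ranges assume that manufacture starts at leukapheresis and that dosing follows at once. The conclusion needs only the lower end, which is about 6 weeks on every reading.

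The effect is confined to attribution in at most 10 patients, where one misread patient is 1/10 = 10% of the sample. The primary analysis, the stopping rule and withdrawal decisions are unaffected. How many patients would be misread cannot be estimated from the documents, because it would need spontaneous change rates and the correlation among the four markers.

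**What to change.** In Section 10.3, define on-treatment shift as change from the Injection Week #1 pre-dose value to Injection Week #3, the Nephrectomy Visit and End of Study, using Screening only if the pre-dose value is missing. Report Screening to Injection Week #1 separately, labelled as pre-treatment change.

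Reconcile the Screening window in Section 8.2 with note 1 of Table 1, and the heading of Section 8.3 with the sentence beneath it, so that the interval can be stated.

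The cost is wording only. No sample, visit or patient is added, and the clinical follow-up described in Section 10.3 is unchanged.

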10.4 Injection Site Reaction and Post-Dose Vital Signs Evaluation

Injection sites will be examined for reactions and vital signs assessed 1 hour following AGS-003 administration, while the subject remains in the clinic. Subjects will also be instructed to conduct self-examinations of the injection sites and to contact study staff if a reaction occurs or worsens after a study visit. Mild and moderate ISRs are expected and should resolve without sequelae. Injection site reactions should not be treated with any form of corticosteroids or antihistamines. If desired, non-steroidal anti-inflammatory drugs (NSAIDS) such as ibuprofen may be used to alleviate symptoms.

10.5 Adverse Events

10.5.1 Definition

An adverse event or adverse experience (AE) is any untoward medical occurrence associated with the use of a drug in humans, whether or not considered drug related. Therefore, an AE can be ANY unfavorable and unintended sign (including an abnormal laboratory finding, if clinically significant), symptom, or disease temporally associated with the use of a medicinal (investigational) product, whether or not considered related to the medicinal (investigational) product (attribution of ‘unrelated’, ‘unlikely’, ‘probable’, or ‘definite’).

An AE is considered “unexpected” if it is not listed in the investigator brochure or is not listed at the specificity or severity that has been observed; or if an investigator brochure is not required or available, is not consistent with the risk information described in the general investigational plan in other study-related documents.

10.5.2 Diagnosis Versus Signs and Symptoms

If known, a diagnosis should be recorded on the CRF rather than individual signs and symptoms (e.g., record only liver failure or hepatitis rather than jaundice, asterixis, and elevated transaminases). However, if a constellation of signs and/or symptoms cannot be clinically characterized as a single diagnosis or syndrome at the time of reporting, each individual event should be recorded as an AE or SAE on the CRF. If a diagnosis is subsequently established, it should be reported as follow-up information.

10.5.3 Adverse Events Occurring Secondary to Other Events

In general, AEs occurring secondary to other events (e.g., cascade events or clinical sequelae) should be identified by their primary cause. For example, if severe diarrhea is known to have resulted in dehydration, it is sufficient to record only diarrhea as an AE or SAE on the CRF.

However, clinically significant AEs occurring secondary to an initiating event that are separated in time should be recorded as independent events on the CRF. For example, if a severe gastrointestinal hemorrhage leads to renal failure, both events should be recorded separately on the CRF.

